## 10 STATISTICAL CONSIDERATIONS

### 10.1 Statistical and Analytical Plans

A formal statistical and analytical plan (SAP) will be completed prior to database lock and unblinding of the study data.

### 10.2 Statistical Hypotheses

All statistical analyses for all safety and efficacy endpoints will be descriptive summary statistics. Subjects who received placebo will be pooled across cohorts. Safety data will be evaluated by assessing the various dose groups of EB-001 versus the placebo group.

### 10.3 Analysis Datasets

The *safety set* will include all randomized subjects who received at least 1 dose of study drug and have at least 1 safety assessment thereafter.

The *efficacy set* will include all randomized subjects who received at least 1 dose of study drug and have at least 1 efficacy assessment thereafter.

### 10.4 Description of Statistical Methods

#### 10.4.1 General Approach

Data will be summarized by dose of EB-001, across all subjects who received EB-001, and across all subjects who received placebo.

All continuous variables will be summarized using descriptive statistics of mean, median, standard deviation, minimum, and maximum. Categorical variables will be summarized using descriptive statistics of number and percentage of patients in each category.

#### 10.4.2 Analysis of the Primary Efficacy Endpoint(s)

Baseline characteristics and change from baseline (CBL) of Investigator's assessment of GL severity at maximum using the FWS will be summarized using descriptive statistics, with details provided in patient listings.

## 10.4.4 Safety Analyses

### 10.4.4.1 Demographics and Baseline Characteristics

Demographic and baseline characteristics (medical history, physical examination, prior medications) will be summarized using descriptive statistics, with details provided in patient listings.

### 10.4.4.2 Prior and Concomitant Medications

All prior and concomitant medications will be assigned a generic name and a drug class based on the World Health Organization (WHO) Dictionary. Prior and concomitant medications will be listed and summarized by drug class.

### 10.4.4.3 Completion of the Study and Withdrawals

Withdrawals and the reason for withdrawal (AE(s), protocol non-compliance, lost to follow-up, failed to return, did not meet entrance criteria, voluntary withdrawal, and other reasons) will be tabulated. The number and percentage of subjects who complete the study and who withdraw from the study will be tabulated.

### 10.4.4.4 Tolerability Analysis

Tolerability will be assessed at each dose level of EB-001/placebo by tabulating the number and percentage of subjects who develop one or more of the toxicity criteria in [Table 3](#). If 2 or more EB-001-treated subjects within a cohort at a particular dose level of EB-001 develop any of the intolerable toxicities specified in [Table 3](#) and if these are considered to be related to EB-001, then that dose level will be considered an intolerable dose. The previous tolerated dose tested will be considered the highest tolerated dose (see [Section 4.1.1](#)).

### 10.4.4.5 Adverse Events

Adverse events will be classified into standard terminology using the Medical Dictionary for Regulatory Activities (MedDRA). Adverse events will be listed by event description (MedDRA-preferred term), dates and times of onset and resolution, clinician's assessment of severity, assessment of relatedness to study drug (either related or not related), and action taken. Additionally, data may be grouped for analysis by different levels of the MedDRA

hierarchy. The incidence of AEs, the incidence of treatment-related AEs, and the severity of AEs will be tabulated

Serious adverse events, treatment-related SAEs (with subsets for SAEs resulting in death and non-fatal SAEs) and subjects who withdraw due to an AE will be tabulated.

#### 10.4.4.6 Clinical Laboratory Tests

Clinical laboratory test parameters will be listed for individual subjects. Baseline for clinical laboratory parameters will be defined as the last evaluation before dosing with study treatment. For each parameter, with the exception of urinalysis parameters, summary statistics, including mean absolute change from baseline, will be calculated for each measure and summarized; urinalysis results will be listed but not summarized. In addition, for leukocyte and lymphocyte counts, percentage change from baseline will be tabulated.

Each clinical laboratory test will be defined to be “Low”, “Normal”, or “High”, according to the normal reference range from the clinical laboratory. The number and percentage of subjects who have a shift from within to outside the normal reference range (and vice versa) from baseline to each follow-up visit will be summarized.

Each clinical laboratory test will also be assigned to a grade based on the CTCAE v4.03 (CTCAE 2010). The number and percentage of subjects who have Grade 2, Grade 3, or Grade 4 laboratory value will be summarized.

#### 10.4.4.7 Vital Signs

Vital signs results (including BP [systolic and diastolic], pulse rate, and body temperature) will be listed for individual subjects. Baseline for vital signs measurements will be defined as the last evaluation before dosing with study medication. Summary statistics, including mean change from baseline, will be determined for each measure and will be tabulated.

Vital signs will be reviewed for notable abnormalities according to the criteria in Table 6, and clinically notable vital sign abnormalities will be listed. The number and percentage of subjects who have a clinically notable vital sign abnormality will be summarized.

**Table 6** Criteria for Clinically Notable Vital Sign Abnormalities

Parameter	High Threshold	Low Threshold
Systolic BP	>30 mmHg increase from baseline	>30 mmHg decrease from baseline
Diastolic BP	>20 mmHg increase from baseline	>20 mmHg decrease from baseline
Pulse rate	>120 beats/min and an increase in pulse rate of $\geq 15$ beats/min from baseline	<40 beats/min and a decrease in pulse rate of $\geq 15$ beats/min from baseline
Body temperature	>39.0°C (= >102.2°F)	<35.0°C (= <95.0°F)

### 10.4.4.8 Electrocardiograms

ECG intervals/durations (RR, PR, QT, QTcF, and QTcB intervals and QRS duration) and HR will be listed for individual subjects. Baseline for ECG intervals/durations will be defined as the mean of the triplicate values recorded on the last evaluation before dosing with study medication. Summary statistics, including mean change from baseline, will be determined for each measure and will be tabulated.

Electrocardiographic intervals and durations will be reviewed for notable abnormalities according to the criteria in Table 7, and clinically notable abnormalities will be listed. In addition, other ECG findings considered to be clinically significant (for example, rhythm disturbances, conduction abnormalities, T wave/ST segment abnormalities, etc.) will also be listed. The number and percentage of subjects who have a clinically notable ECG interval abnormality or other clinically significant ECG finding will be summarized.

**Table 7 Criteria for Clinically Notable ECG Interval Abnormalities**

Interval/Duration	High Threshold	Low Threshold
PR interval	PR interval $\geq 220$ msec	PR interval $\leq 120$ msec
QRS duration	QRS duration $\geq 120$ msec and an increase in QRS duration of $\geq 20$ msec from baseline	–
QT interval	QT interval $> 500$ msec	–
QT c intervals 	Males: QT c interval $\geq 450$ msec and an increase in QT c interval of $\geq 60$ msec from baseline or QT c interval $> 500$ msec	–
	Females: QT c interval $\geq 470$ msec and an increase in QT c interval of $\geq 60$ msec from baseline or QT c interval $> 500$ msec	

 Fridericia's and Bazett's corrections (QTcF and QTcB, respectively)

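### Table 7 flags PR on a limit alone, so a subject whose PR was already beyond the limit before dosing and has not changed is counted as having a clinically notable ECG abnormality

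*Combined protocol and SAP*

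**What the plan says.** Section 10.4.4.8 and Table 7 set the ECG criteria, and Section 10.4.4.7 with Table 6 sets the vital-sign criteria. They take three forms.

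- **Limit and change.** QRS: "QRS duration $\geq 120$ msec and an increase in QRS duration of $\geq 20$ msec from baseline". Pulse rate in Table 6 and the first part of the QTc criterion work the same way.
- **Limit alone.** PR: "PR interval $\geq 220$ msec" or "PR interval $\leq 120$ msec". QT: "QT interval $> 500$ msec". Body temperature in Table 6. The second part of the QTc criterion is also a limit alone: "msec from baseline or QT c interval $> 500$ msec".
- **Change alone.** Systolic and diastolic blood pressure, for example ">30 mmHg increase from baseline".

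For ECGs the summary rule is: "The number and percentage of subjects who have a clinically notable ECG interval abnormality or other clinically significant ECG finding will be summarized". Section 10.4.4.7 has a parallel sentence for vital signs. Neither sentence limits the count to findings that are new or worse than baseline.

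Section 10.4.4.8 defines the ECG baseline as the mean of the last pre-dose triplicate. It does not say whether a post-dose ECG is judged on its triplicate mean or on single tracings. Section 7.1.1.10 places ECGs at Screening, Day 2 and Day 30, so there is one pre-dose and two post-dose recordings. Section 5.1 sets no numeric PR limit at entry; good health is left to the Investigator's judgement.

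**The concern.** A limit with no reference to baseline counts a fixed trait of the subject as if it were a finding on treatment. It also counts a trivial crossing: 122 msec at Screening and 119 msec on Day 2 is a 3 msec difference, yet it is flagged.

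Section 4.2.1 makes the incidence of abnormal ECG findings a safety endpoint. Section 10.2 compares dose groups with pooled placebo. With 5 subjects per dose and 7 on placebo, one flagged subject is 1/5 = 20% of a dose group or 1/7 = 14% of placebo. Flags that reflect only who was enrolled, or measurement noise, fall at random across doses. They could suggest a dose pattern or blur a real one.

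**Working it through.** **The plan's own figure.** Table 8 gives the chance of at least one event among n subjects, 1 − (1 − p)^n. For n = 5 and p = 0.01, 0.1, 0.2, 0.5 this gives 4.9%, 41.0%, 67.2%, 96.9%. For n = 35 and p = 0.01, 0.1 it gives 29.7% and 97.5%. Table 8 reproduces, and the same formula is used below.

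**The rules applied as written** (baseline to post-dose):

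| Measure | Values | Counted? |
|---|---|---|
| PR | 118 to 118 msec | yes |
| PR | 222 to 222 msec | yes |
| QRS | 125 to 125 msec | no |
| QTc, male | 455 to 455 msec | no |
| Pulse | 125 to 125 beats/min | no |
| QT | 505 to 505 msec | yes |
| QTc | 505 to 505 msec | yes |
| Temperature | 34.9 to 34.9 °C | yes |

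The lack of a baseline reference therefore follows from the text, with no assumption needed.

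**Size for PR with no drug effect.** The documents give no PR mean or variance, so these inputs are assumptions: population mean 150 or 160 msec, between-subject SD 18 or 22, visit-to-visit SD 5 or 8, within-triplicate SD 4. Each visit value is a triplicate mean, so the tracing variance contributes 16/3 = 5.33.

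Hand check for one visit, with total SD = √(between² + visit² + 5.33):

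- Lowest corner (160, 18, 5): √(324 + 25 + 5.33) = 18.82. P(PR ≤120) = Φ(−40/18.82) = 1.68%; P(PR ≥220) = 1 − Φ(60/18.82) = 0.07%. Total 1.8%.
- Highest corner (150, 22, 8): √(484 + 64 + 5.33) = 23.52. P(PR ≤120) = Φ(−30/23.52) = 10.11%; P(PR ≥220) = 1 − Φ(70/23.52) = 0.15%. Total 10.3%.

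A subject is flagged if either Day 2 or Day 30 is beyond a limit. Visits within a subject are correlated, so this step was simulated at all eight corners:

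- Flagged at least once: about 2.5% (2.4% to 2.5% between runs) at the lowest corner, 13.8% at the highest.
- At least one flag among 5: 1 − 0.975^5 = 12%; 1 − 0.862^5 = 52%.
- Expected flags: 35 × 0.025 = 0.9 to 35 × 0.138 = 4.8 on EB-001; 7 × 0.025 = 0.2 to 7 × 0.138 = 1.0 on placebo.
- Flagged although the baseline was within limits, by noise alone: 1.2% to 5.8% of all subjects. Excluding subjects already beyond the limit at baseline would therefore not be enough.
- If single tracings are judged instead of triplicate means: 3.9% to 17.6% flagged.

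**With a change also required.** Using the QRS row's 20 msec as an illustration, in the direction of the limit crossed, flags fall to about 0.06% to 1.9%. The chance of at least one among 5 becomes 1 − 0.9994^5 = 0.3% to 1 − 0.981^5 = 9.1%.

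**The case against.** The strongest reply is that nothing in the plan requires all rows to share one form, and that a reader can see through a spurious flag. Individual values are listed, mean change from baseline is tabulated, data are also summarized across all EB-001 subjects, and no-effect flags arise on placebo too. With about 42 subjects, the baseline behind each flag can be checked by hand. This stands and keeps the point small. It does not make the summary count right: the listings show the error but the percentages still carry it.

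Four stronger readings are tempting, and the documents do not support them.

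- *PR alone departs from a two-part standard.* It does not. QT, body temperature and QTc above 500 msec are also limit-only.
- *The blood pressure rows are faulty in the mirror sense and need an absolute level.* A change-only flag may be intended in a first-in-human study. Section 2.3.1 lists a sudden drop in blood pressure among the signs of a life-threatening allergic reaction. In a simulated one-visit fall of 35/20 mmHg, illustrative absolute limits cut the share of subjects flagged from 77-79% to 64-65%, so adding a level has a real cost.
- *PR flags would dominate the ECG count.* This was not tested. No other interval, and no rate of other clinically significant findings, was modelled.
- *Dose decisions could be distorted.* Section 10.4.4.4 judges tolerability on Table 3, which uses seriousness and CTCAE grade, not Table 7. Part of Section 4.1.1 is redacted, so this rests on the visible text.

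**Conclusion.** The point holds for PR as a minor defect in how a safety summary is counted. That an unchanged out-of-limit PR is counted is certain from the text. The size is not: 2.5% to 13.8% of subjects, or a 12% to 52% chance of at least one flag in a dose group, rests wholly on assumed PR means and SDs and on judging triplicate means. The lack of a new-or-worsened rule also applies to QT, QTc above 500 msec and body temperature; their flag rates were not estimated. All analyses are descriptive, so no test or error rate is affected.

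**What to change.** Section 10.1 has the SAP completed before database lock and unblinding, so the change can be made there.

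1. Count a PR flag in the summary only if the post-dose value is beyond the limit **and** has moved from the baseline triplicate mean by a pre-stated margin, as in the QRS row. The sponsor sets the margin; the 20 msec above is an illustration borrowed from a different interval.
2. For QT, QTc above 500 msec and body temperature, report flags separately as new or worsened versus present at baseline.
3. State that post-dose ECGs are judged on the triplicate mean, so that both sides of the comparison are built alike.

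The blood pressure rows need no change, although a sentence saying that the change-only form is intended would help.

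The cost is one table row and a few sentences, with no new data: Screening triplicates are already collected. The downside is that subjects who meet only the limit leave the summary count, including a real but small shift (PR 205 to 222 msec moves 17 msec and would not meet a 20 msec margin). They stay in the listings and can still be reported as adverse events or clinically significant ECG findings.

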### 10.4.4.9 Physical and Focused Neurological Examinations

Findings of physical and focused neurological examinations will be listed for individual subjects and summarized.

For the evaluation of SOT terms, the criteria for Grading are:

- Grade 1 (Mild): Asymptomatic or mild symptoms; clinical or diagnostic observations only; intervention not indicated.
- Grade 2 (Moderate): Minimal, local or noninvasive intervention indicated; limiting age-appropriate instrumental Activities of Daily Living (ADL). Instrumental ADL refer to preparing meals, shopping for groceries or clothes, using the telephone, managing money, etc.
- Grade 3 (Severe or medically significant but not immediately life-threatening): Hospitalization or prolongation of hospitalization indicated; disabling; limiting self-

care ADL. Self-care ADL refer to bathing, dressing and undressing, feeding self, using the toilet, taking medications, and not bedridden

- Grade 4 (Life-threatening consequences): Urgent intervention indicated.
- Grade 5 (Death related to AE).

#### **10.4.4.11 Urine Drug Test**

Results of urine drug test will be listed for individual subjects. Each test will be defined to be “negative” or “positive”, according to the normal reference range from the clinical laboratory. The number and percentage of subjects who are “positive” or “negative” in each visit will be summarized.

#### **10.4.4.12 Pregnancy Test**

Results of pregnancy test will be listed for individual subjects. Each test will be defined to be “negative” or “positive”, according to the normal reference range from the clinical laboratory. The number and percentage of subjects who are “positive” or “negative” in each visit will be summarized.

#### **10.4.5 Planned Interim Analyses**

No formal interim analysis is planned.

#### **10.4.6 Exploratory Analyses**

Exploratory analyses of efficacy as appropriate may be conducted.

### **10.5 Sample Size**

This is the first human study to evaluate the safety and efficacy of EB-001, and therefore there are no data on which to base sample sizes. However, a sample size of 5 subjects per

cohort (n = 5 EB-001, n = 1 placebo) is considered to provide sufficient initial information on the estimation of the safety and tolerability of EB-001.

With 5 subjects receiving each dose level of EB-001 per cohort, an AE that occurs with a true frequency of 50% will be detectable with 96.9% probability within a given cohort. Combined across cohorts, with 35 subjects receiving EB-001, an AE that occurs with a true frequency of 10% will be detectable with greater than 97.5% probability. The probability of detecting AEs is shown in [Table 8](#):

**Table 8 Probability of Detecting Adverse Events that Occur at Various Frequencies**

True Event Rate	Probability of Observing at Least 1 Event with 5 Completed Subjects	Probability of Observing at Least 1 Event with 35 Subjects
0.01	4.9%	29.7%
0.1	41.0%	97.5%
0.2	67.2%	>99%
0.5	96.9%	>99%

## 10.6 Measures to Minimize Bias

### 10.6.1 Enrollment/ Randomization/ Blinding Procedures

Subjects who meet the enrollment criteria will be enrolled into sequential cohorts. Patients are considered to be randomly assigned to the study when they are assigned to receive either EB-001 or placebo. Within each cohort, subjects will be randomly allocated to receive either EB-001 or placebo in a 5:1 ratio. The dosage level of EB-001 will not be randomized.

The study will be conducted in a double-blinded manner. Study drugs between EB-001 and the placebo vials will be identical in appearance. Study site personnel who prepare the study drug will not be involved in safety and efficacy assessment.

There will be an unblinded independent dispenser who will prepare and dispense EB-001 or placebo for administration in a blinded manner to subjects. The Investigator and site personnel, study subjects, and Sponsor personnel will be aware of the EB-001 dose level in each dose cohort; however, except for a limited number of Sponsor staff (see below), they will be unaware of whether subjects are receiving EB-001 or placebo until the study is formally unblinded.

#### 10.6.1.1 Subject Numbering

Patients who have signed the ICF to begin screening procedures will be entered into the electronic data capture (EDC) system. The site will assign a 3-digit site-specific sequential screening number at that time. The unique patient identification number will consist of a

3-digit original site number followed by a 3-digit screening number. The patient will keep the same number throughout the study. Upon randomization, a unique 4-digit study-specific randomization number will be assigned by an Interactive Voice Response System (IVRS) or Interactive Web Response System (IWRS) system.

In the rare circumstance, where a patient is randomly assigned to treatment but does not receive the study drug, the study coordinator/research nurse must immediately inform the IVRS or IWRS that the study drug was not administered.

## **10.6.2 Evaluation of Success of Blinding**

### **10.6.2.1 Blinding at the Study Site**

Study treatment group information (active drug vs placebo) will remain blinded to the subject and also to all blinded members of the study team at the study site. There will be an unblinded independent dispenser who will prepare and dispense EB-001 or placebo for administration in a blinded manner to subjects. Study site personnel who prepare the study drug will not be involved in safety and efficacy assessment.

Investigators, coordinators, and nurses who are responsible for reviewing potentially unblinded medical data or who may have access to it (including all routine laboratory tests, imaging, and AEs) must not discuss any unblinded information or results with the site personnel responsible for blinded study assessments.

### **10.6.2.2 Blinding of Sponsor Personnel**

During this study, staff of Bonti and designee will be blinded to treatment allocation, except as described in this section. The periodic DRT reviews will be performed in a blinded manner unless the data warrant unblinding due to safety concerns. It is assumed that the need to unblind a study subject's treatment assignment will occur in the setting of an SAE, and therefore, all procedures for the reporting of a SAE must be followed (see [Section 8.5.1](#)).

Procedures for emergency unblinding are described in [Section 10.6.3](#). These procedures ensure that neither study blinded monitoring staff nor the Investigator and other site staff who are blinded have premature access to the study subjects' treatment assignments. Any personnel from Bonti and designee who become unblinded to study safety and efficacy data will be documented and no longer participate in day-to-day management of the study.

## **10.6.3 Breaking the Study Blind/Participant Code**

An Investigator at a site may break the blind in the event of an immediate medical emergency, where knowledge of the study subject's treatment assignment (EB-001 or placebo) must be known in order to facilitate appropriate emergency medical treatment. In

these situations, the Investigator must first attempt to contact the Medical Monitor or designee before unblinding a subject's treatment identity in order to obtain concurrence that unblinding a study subject's treatment assignment is necessary. If circumstances preclude contacting the Medical Monitor or designee, each instance of unblinding must be reported to Sponsor within 24 hours. The Medical Monitor or designee may break the blind internally in the event of SAE(s), which require expedited reporting to regulatory authorities. Any other requests to reveal a subject's treatment identity must be requested of, and approved by the Medical Monitor or designee. If a study subject's treatment identity is unblinded by the study site, the unblinding must be reported to Bonti and documented on the eCRF as a deviation. If a subject's treatment identity is unblinded, the subject will be withdrawn from the study and will complete the Early Termination procedures describe in [Section 5.4](#).

In an emergency situation in which the Investigator believes that the identity of a study subject's treatment assignment is necessary to treat the subject, the study subject's treatment assignment may be obtained from the 24-hour IVRS/IWRS. Details of the process to be followed and the telephone number are provided in the study manual(s) provided to the site. In the event that the IVRS/IWRS is used to perform a code break, Bonti or designee will be notified immediately by the IVRS/IWRS using an automated notification.

The Investigator or designee is responsible for ensuring that the instructions on how to perform a code break are stored safely, that their location is known, and that access is readily available to the relevant staff in case of an emergency.

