## 2.2 Rationale

### 2.2.1 Study Rationale

This will be the FIH study of EB-001 to measure safety and efficacy in GL. Single doses of EB-001 administered through IM injection into procerus at midline and the medial and lateral corrugators will be assessed in healthy subjects with glabellar frown lines.

A total of 7 ascending dose cohorts are planned, or up to 9 cohorts if 2 additional cohorts are evaluated. Each dose cohort will enroll a total of 6 subjects randomized to receive either EB-001 or placebo in a ratio of 5 (active): 1 (placebo).

[REDACTED]

[REDACTED]

[Redacted]

[Redacted]

[Redacted]

[Redacted]

[Redacted]

- [Redacted]
- [Redacted]

[Redacted]

[Redacted]

[Redacted]

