#### **4.1.2 Follow-up of Subjects Meeting Stopping Criteria**

Subjects with any of the criteria in [Table 3](#) will be monitored carefully, which may include the following (to be agreed upon by the Investigator and the Medical Monitor):

- Additional clinical laboratory tests and/or other investigations.
- Additional outpatient visits.
- Extended duration of follow-up.
- Obtaining a specialist's opinion.

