### **7.1.1.5 Assessment of Adverse Event**

Adverse events will be recorded beginning after signing the ICF until completion of the study until the final follow-up visit (Day 42), and will be evaluated by the Investigator for severity (using CTCAE version 4.03 criteria ([CTCAE 2010](#))), seriousness, and attributability to study medication. Further details on AEs, including definitions, elicitation, and reporting are provided in [Section 8](#).

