## 8.4 Reporting Procedures

### 8.5 Adverse Event Reporting

All AEs, *whether or not related to the study drug*, must be fully and completely documented on the AE eCRF and in the subject's medical notes. The following attributes must be assigned: event description, dates and times of onset and resolution, clinician's assessment of severity, assessment of relatedness to study drug (either related or not related), and action taken. The Investigator may be asked to provide additional follow-up information.

In the event that a subject is withdrawn from the study because of an AE, it must be recorded on the eCRF. The subject must be followed and treated by the Investigator until the AE has resolved, stabilized, or a new chronic baseline has been established.

The Investigator must report all observed AEs and all reported AEs. At each visit the Investigator will ask the subject a nonspecific question (e.g., "Have you noticed anything different since your last visit?") to assess whether any AEs have been experienced since the last report or visit. AEs will be identified and documented on the AE page of the eCRF in appropriate medical terminology. The severity and the relationship to the study drug will be determined and reported on the eCRF (see [Sections 8.1.1](#) and [8.2.2](#)).

Note that any intermittent or as-needed ("PRN") use of medication (and specifically any newly prescribed medication) during the course of a study may indicate the occurrence of an AE that may need to be recorded on both the AE page of the eCRF and the Concomitant Medication page.

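### Section 10.6.3 withdraws every unblinded subject, which in a single-dose study ends the scheduled search for new or later safety events without sparing any exposure

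*Combined protocol and SAP*

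**What the plan says.** Section 10.6.3 sets the consequence of a code break: "If a subject's treatment identity is unblinded, the subject will be withdrawn from the study and will complete the Early Termination procedures". It refers to Section 5.4 for those procedures, and Section 5.4.2 describes evaluations reaching only as far as the withdrawal date.

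Three routes to unblinding are foreseen:

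- The investigator may break the code in an immediate medical emergency, after first trying to reach the Medical Monitor (Section 10.6.3).
- The sponsor may do so for reporting: "The Medical Monitor or designee may break the blind internally in the event of SAE(s), which require expedited reporting to regulatory authorities" (Section 10.6.3).
- The Data Review Team may be unblinded: "The periodic DRT reviews will be performed in a blinded manner unless the data warrant unblinding due to safety concerns" (Section 10.6.2.2).

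The same Section 10.6.2.2 gives the expected setting: "It is assumed that the need to unblind a study subject's treatment assignment will occur in the setting of an SAE".

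Other sections govern follow-up of events. Section 8.5, on subjects for whom an AE is the reason for withdrawal, says: "The subject must be followed and treated by the Investigator until the AE has resolved, stabilized, or a new chronic baseline has been established". Sections 8.3 and 8.5.1 also require events and SAEs to be followed to an outcome. Section 4.1.2 lists "Extended duration of follow-up" among the optional measures for subjects who meet a Table 3 toxicity criterion.

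No section says that the scheduled visits to Day 42 continue after a code break.

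**The concern.** Withdrawal after unblinding can make sense when treatment is ongoing. Here there is one treatment session (Sections 2.2.1 and 7.1.1.18), so nothing is left to stop and withdrawal only ends observation.

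The subjects affected are not a random subset. By the protocol's own expectation they are people with an SAE, so the missing later data are likely to be informative. Following a known event to its outcome differs from examining a subject on schedule for spread of toxin, laboratory changes or ECG changes that have not yet appeared.

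The dose decision can be sensitive to a single subject. Section 10.4.4.4 calls a dose intolerable when two or more EB-001 subjects in a cohort have related Table 3 toxicities. An SAE judged unrelated does not count (Table 3, footnote 1). A subject unblinded for such an SAE would leave scheduled observation, and a later related toxicity, which could decide the count, would be less likely to be found.

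**Working it through.** **Inputs**

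- Post-dose visits: Days 1, 2, 7, 14, 30 and 42, each with a focused neurological examination (Section 7.1.1.8).
- Post-dose ECG: Days 2 and 30 (Section 7.1.1.10). Laboratory tests and urinalysis: Days 7 and 30 (Sections 7.1.1.12 and 7.1.1.13).
- Vital signs and Facial Wrinkle Scale (FWS): every visit to Day 30 (Sections 7.1.1.11, 7.1.1.20 and 7.1.1.21). AE recording: to Day 42 (Section 7.1.1.5).
- Subjects on EB-001: 5 per cohort, 35 over seven cohorts (Section 10.5).
- Assumptions: the Early Termination (ET) visit takes place on the day of the code break, that day's scheduled assessments are already done, and the ET visit carries the Day 30 set, as the shared EOS/ET label suggests.

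**Step 1: reproduce Table 8.** P(at least one event) = 1 − (1 − p)^n.

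- n = 5, p = 0.01, 0.1, 0.2, 0.5: 4.90%, 40.95%, 67.23%, 96.88%.
- n = 35, same rates: 29.66%, 97.50%, 99.96%, >99.99%.

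These agree with the printed values.

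**Step 2: scheduled follow-up lost, by day of code break** (days lost = 42 − day of break)

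| Code break | Later visits dropped (of 6) | Days lost (of 42) |
|---|---|---|
| Day 1 | 5 | 41 (98%) |
| Day 2 | 4 | 40 (95%) |
| Day 7 | 3 | 35 (83%) |
| Day 14 | 2 | 28 (67%) |
| Day 30 | 1 | 12 (29%) |

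**Step 3: what a Day 2 code break costs, net of the ET visit**

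- Neurological examinations: 4 still due, 1 done at ET, net loss 3.
- Vital signs and FWS: 3 still due (Days 7, 14, 30), 1 done, net loss 2.
- Laboratory tests: 2 still due (Days 7, 30), 1 done, net loss 1.
- ECG: 1 still due (Day 30), 1 done, net loss 0, but taken 30 − 2 = 28 days early.

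The main loss is in the neurological examinations and in the timing of everything else.

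**Step 4: effect on detecting a later event.** One of 5 active subjects is 20% of that dose's later data. Suppose the subject is not replaced and the event would begin after the ET visit. Then n falls from 5 to 4:

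| True rate | n = 5 | n = 4 |
|---|---|---|
| 0.01 | 4.9% | 3.9% |
| 0.1 | 41.0% | 34.4% |
| 0.2 | 67.2% | 59.0% |
| 0.5 | 96.9% | 93.8% |

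At a 10% rate: 1 − 0.9^5 = 40.95% and 1 − 0.9^4 = 34.39%, a drop of about 6.6 percentage points. Pooled over all doses the effect is slight: with 34 instead of 35 subjects, 97.5% becomes 97.2%.

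**Step 5: do the follow-up sections close the gap?** Sections 8.3, 8.5 and 8.5.1 follow events that have been identified. Section 8.5.1 also accepts reports of possibly product-related SAEs for 30 days after the follow-up period. Section 4.1.2 offers further visits and tests at discretion. None restores the fixed schedule. Section 8.5 is also tied to an AE as the reason for withdrawal, whereas under Section 10.6.3 the reason is the unblinding. Section 5.4.2 bars replacement when a Table 3 criterion is the cause, without saying how an unblinding after an SAE is classed.

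**The case against.** The strongest reply is that the protocol already protects these subjects and that few, if any, will be affected. Much of that stands, and several stronger readings should be set aside.

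- *Safety follow-up as a whole stops.* A reader might infer this from the withdrawal sentence. It does not: the triggering event must still be followed to an outcome under Sections 8.3, 8.5 and 8.5.1.
- *Section 10.6.3 contradicts Sections 8.5 and 4.1.2.* Section 8.5 presupposes withdrawal and adds follow-up after it, and Section 4.1.2 is optional. They complement the rule more than they contradict it, although how they fit together is left unstated.
- *Subjects with the most serious events are withdrawn as a class.* Section 10.6.2.2 says that unblinding, if needed, is expected around an SAE. It does not say that an SAE leads to unblinding. Site code breaks are confined to emergencies, and sponsor or Data Review Team unblinding is discretionary.
- *Early ET values will be reported as Day 30.* The shared label invites the question, but the schedule table is not visible and the formal SAP is to be completed later (Section 10.1). The documents do not show how ET data will be mapped.
- *Withdrawn subjects leave the analysis.* Section 10.3 keeps any dosed subject with one relevant post-dose assessment in the safety or efficacy set.

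The scope of the sentence can also be disputed. The sentence before it concerns unblinding by the site, so a narrower intent is possible. As written, however, it contains no such limit.

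One rationale for the rule is fair: it keeps ratings made with knowledge of treatment out of the data. Identifying those ratings serves that purpose without losing the safety observations.

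**Conclusion.** The point holds in a limited form. Followed as written, Section 10.6.3 gives up scheduled detection of new or later events in subjects likely to have had a serious event, and it prevents no exposure in return. The triggering event itself is not lost to follow-up.

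For each early code break the size is up to 4 of 6 post-dose visits after Day 2. If the subject is on EB-001 and not replaced, detection at that dose falls from 41.0% to 34.4% for a later event with a 10% true rate. These figures assume an ET visit on the day of the break, independent events and onset after that visit. They do not apply to a placebo subject, and replacement would bring the dose group back to five.

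The documents give no expected number of code breaks, and none may occur among about 42 subjects. The rule should be corrected because it is explicit and cheap to change, but it does not endanger the trial's main conclusions.

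**What to change.** - In Section 10.6.3, replace the withdrawal sentence with a statement that unblinding does not by itself end participation, and that an unblinded subject who still consents continues the scheduled data collection to Day 42. State that this applies whoever breaks the code. The change concerns data collection only.
- Record the date of each code break, the reason for it and who made it.
- In the SAP, flag FWS ratings and AE causality assessments made after the break by anyone aware of the assignment, and repeat the descriptive efficacy summary without the flagged ratings.
- Reconcile Section 10.6.3 with Sections 4.1.2, 5.4.2, 8.3, 8.5 and 8.5.1, so that it is clear which follow-up applies after unblinding and how replacement is handled.

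The cost is one replaced sentence, a few cross-references and a short SAP entry. The downside is a small number of FWS and causality ratings made unblinded. Because all analyses are descriptive (Section 10.2), the flag and the repeated summary deal with this adequately.
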